- On Day 1, study personnel must verify the following pre-dose assessments to be within normal limits prior to injection: triplicate 12-lead ECG, brief physical exam, vital signs, pregnancy test (negative; FRP only), AE assessment, and concomitant medication assessment. If a clinical abnormality, clinically significant AE, or prohibited medication that precludes injection is observed/recorded, the medical monitor must be contacted for further instruction.
- Participants may be admitted to the clinic before Injection 1 Day 1 and Injection 2 Day 1. Any new Phase I unit participating in this study will adhere to the following SARS-CoV-2 testing procedures. **Where SARS-CoV-2 is circulating in the community**, participants should have one SARS-CoV-2 test approximately 1 week prior to admission to the clinic. A second test would be done upon admission; prior to the test result being known, participants should follow strict infection control procedures (PPE/social distancing) and should be isolated within an area of the unit to avoid exposure to COVID-19 negative participants until the test result is known. Once the test result is a confirmed negative, they can be released into the unit and follow infection control practices as per unit guidance. Any new Phase I unit participating in this study will adhere to the following SARS-CoV-2 testing procedures. A further test will be done on Day 8 upon discharge from the clinic. **Where SARS-CoV-2 is NOT circulating in the community**, SARS-CoV-2 testing prior to dosing may be performed within 5 days of admission to the clinic, and if participants are not admitted, they will be advised to avoid exposure to COVID-19 and self-quarantine until entrance to the unit while awaiting final testing clearance. Sponsor approval is required for site(s) to adopt SARS-CoV-2 testing within 5 days of admission to the clinic if study participants do not remain and isolate within the unit until test results are known. A further test is NOT required on Day 8 upon discharge from the clinic. Participants may have some assessments, such as HIV test, drug/alcohol screen, pregnancy test, haematology/chemistry/urinalysis and coagulation tests, done on the day before Injection 1 Day 1 and Injection 2 Day 1.
- CAB 400 mg/mL - injection 1 loading dose of 300 mg and injection 2 300 mg Q4W SC.

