2.3.1. Risk Assessment

Potential Risk of Clinical Significance	Summary of Data/Rationale for Risk	Mitigation Strategy
	Investigational Product (IP) CAB [GSK 1265744]	
Drug Induced Liver Injury (DILI)	
A small proportion of participants in the CAB program to date (total exposure approximately 1909 people; 3640 person years to 31 December 2018) have developed transaminitis (elevated liver transaminases characterised by predominant alanine aminotransferase (ALT) elevation). In most participants, transient transaminitis was explained by viral hepatitis infection. In a small number of participants, there was not an alternative explanation, suggesting a mild form of drug induced liver injury (DILI) without hepatic dysfunction, which resolved upon withdrawal of treatment with CAB. All six participants with suspected DILI identified in HIV treatment/ drug-drug interaction (DDI) studies, were received oral CAB, as of 13 January 2019.
	
Exclusion criteria (Section 5.2) will prohibit participants with i) an elevated ALT >1.5x ULN or ii) a bilirubin >1.5xULN (isolated bilirubin >1.5xULN is acceptable if bilirubin is fractionated and direct bilirubin <35 or iii) a current or chronic history of liver disease, or known hepatic or biliary abnormalities from participation in the study
 
A 4-week oral lead-in Phase is being implemented in this study, where all participants will receive oral CAB prior to the administration of IM CAB to assess individual safety and tolerability
 
Liver transaminases (ALT and AST) will be monitored throughout this study (refer to SoA) and the liver chemistry stopping criteria will be adopted (Section 7.1.1).
 
Sentinel dosing in Cohorts 5 & 6 and staggered dosing is included in Cohorts 5 & 6
 
Additional liver biochemistry monitoring is included during the injection phase.
 
If any of the stopping criteria related to liver biochemistry are met in Cohorts 5 or 6 further dosing will be paused pending VSLC review (see Section 7.1).

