- Any participant developing a grade 2 or higher rash with concurrent fever, AST/ALT elevation or eosinophilia prior to the follow-up phase will be withdrawn from study intervention.

During the injection phase of the study, reasons for pausing recruitment or dosing of a cohort following review of safety data or Study Team Review are outlined below. Approval to recommence recruitment to or dosing of a cohort following a pause would be given by the ViiV Healthcare Safety and Labelling Committee (VSLC). In the event of a pause of dosing in the injection phase, the washout period may be extended if deemed necessary by the investigator and sponsor.

- 25% of participants receiving GSK1265744 have a grade 3 or higher AE or laboratory abnormality (with the exception of asymptomatic Grade 3 or higher cholesterol, triglyceride or CPK increase) prior to the follow-up phase or a \geq Grade 2 rash with concurrent fever, AST/ALT elevation or eosinophilia prior to the follow-up phase, where the AEs are considered related to IP in the opinion of the investigator and sponsor.

- If greater than 40% of injections administered within a single cohort are followed by a local injection site reaction of at least grade 2 in severity (once half of cohort participants have received one or more injections).¹⁷
- If $\geq 20\%$ of injections given within a single cohort are followed by an injection site reaction of at least grade 3 in severity (once half of cohort participants have received one or more injections).¹⁷
- If liver chemistry stopping criteria (see Section 7.1.1) are met in a participant in Cohort 5/6.
- If a Cohort 5/6 participant has abnormal liver chemistries not meeting protocol-specified stopping rules, the investigator believes study intervention discontinuation is in the best interest of the participant.
- If a Cohort 5/6 participant develops a grade 2 or higher rash with concurrent fever, AST/ALT elevation or eosinophilia prior to the follow-up phase and is withdrawn from study intervention.

During the long acting phase of the study reasons for stopping the study following Study Team Review are outlined below:

There is a participant death assessed as related to study drug by the principal investigator and sponsor.

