7.1.1. Liver Chemistry Stopping Criteria

Liver chemistry stopping, and increased monitoring criteria have been designed to assure participant safety and evaluate liver event etiology ([across oral and injection phases] in alignment with the FDA premarketing clinical liver safety guidance).

[figure not shown]
<http://www.fda.gov/downloads/Drugs/GuidanceComplianceRegulatoryInformation/Guidances/UCM174090.pdf>

Discontinuation of study intervention for abnormal liver tests is required when:

¹⁷ Where a cohort includes administration via different routes, the ISR data will be considered by each route of administration.

- a participant meets one of the conditions outlined in the algorithm
- in the presence of abnormal liver chemistries not meeting protocol-specified stopping rules, the investigator believes study intervention discontinuation is in the best interest of the participant.

Liver Chemistry Stopping Criteria – Liver Stopping Event Algorithm

Abbreviations: ALT = alanine transaminase; INR = international normalized ratio; SAE = serious adverse event; ULN = upper limit of normal.

Refer to [Appendix 6](#) for required Liver Safety Actions and Follow up Assessments.

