8.2.4. Clinical Safety Laboratory Assessments

- Refer to [Appendix 2](#) for the list of clinical laboratory tests to be performed and to the SoA for the timing and frequency.
- The investigator must review the laboratory report, document this review, and record any clinically relevant changes occurring during the study in the AE section of the CRF. The laboratory reports must be filed with the source documents. Clinically significant abnormal laboratory findings are those which are not associated with the underlying disease, unless judged by the investigator to be more severe than expected for the participant's condition.
- All laboratory tests with values considered clinically significantly abnormal during participation in the study should be repeated until the values return to normal or baseline or are no longer considered significantly abnormal by the investigator or medical monitor.
- If such values do not return to normal/baseline within a period of time judged reasonable by the investigator, the aetiology should be identified, and the sponsor notified.

- All protocol-required laboratory assessments, as defined in [Appendix 2](#), must be conducted in accordance with the laboratory manual and the SoA.
- **Screening for SARS-CoV-2:** Study participants will be monitored at Screening and daily while inpatients for COVID-19 symptoms. Investigator(s) should utilise the World Health Organization (WHO) Case Definitions to classify COVID-19 cases [[World Health Organization](#), 2020]. While outpatients, participants should report to the unit any symptoms suggestive of COVID-19. All participants who experience symptoms suggestive of COVID-19 should be isolated in the unit or at home and tested for SARS-CoV-2 using an approved molecular test (PCR) or an immunological test for a viral antigen. The investigator should consider any participant testing positive for SARS-CoV-2 being discontinued from study drug if COVID-19 symptoms are moderate to severe. Appropriate contact tracing for all participants testing positive will be performed within the unit. This should be done in accordance with local legislation and guidelines. Appropriate follow up should be implemented for participants who discontinue the study due to COVID-19.

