11.6. Appendix 6: Liver Safety: Required Actions and Follow-up Assessments

Phase 1 Liver chemistry stopping criteria have been designed to assure participant safety and to evaluate liver event aetiology

Phase 1 liver chemistry stopping criteria and required follow up assessments

Liver Chemistry Stopping Criteria	
ALT-absolute	
ALT\geq3xULN
 
If ALT\geq3xULN AND bilirubin^{1,2} \geq 2xULN (>35% direct bilirubin) or international normalized ratio (INR) >1.5, Report as an SAE.
 
See additional Actions and Follow Up Assessments listed below

Required Actions and Follow up Assessments	
Actions	Follow Up Assessments

 • Immediately discontinue study intervention • Report the event to GSK within 24 hours • Complete the liver event CRF, and complete an SAE data collection tool if the event also meets the criteria for an SAE² • Perform liver event follow up assessments • Monitor the participant until liver chemistries resolve, stabilise, or return to within baseline (see MONITORING below) 
MONITORING:
 
If ALT\geq3xULN AND bilirubin \geq 2xULN or INR >1.5
 
 • Repeat liver chemistries (include ALT, aspartate transaminase [AST], alkaline phosphatase, bilirubin and INR) and perform liver event follow up assessments within 24 hours • Monitor participant twice weekly until liver chemistries resolve, stabilise or return to within baseline • A specialist or hepatology consultation is recommended 	
 • Viral hepatitis serology³ • Obtain INR and recheck with each liver chemistry assessment until the transaminases values show downward trend • Obtain blood sample for pharmacokinetic (PK) analysis, obtained CAB of last dose⁴ • Serum creatine phosphokinase (CPK) and lactate dehydrogenase (LDH). • Fractionate bilirubin, if total bilirubin\geq2xULN • Obtain complete blood count with differential to assess eosinophilia • Record the appearance or worsening of clinical symptoms of liver injury, or hypersensitivity, on the AE report form • Record use of concomitant medications on the concomitant medications report form including acetaminophen, herbal remedies, other over the counter medications. • Record alcohol use on the liver event alcohol intake case report form

Liver Chemistry Stopping Criteria	

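### Cohort 4b: the pre-dose liver panel at Injection 2 need not be read before dosing, although ALT ≥3×ULN is a mandatory stop

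*Protocol*

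**What the plan says.** **The check before injection.** Footnote 2 of section 1.3.3 names the items to be verified as normal before each Cohort 4b injection: "triplicate 12-lead ECG, brief physical exam, vital signs, pregnancy test (negative; FRP only), AE assessment, and concomitant medication assessment". If a problem that rules out the injection has been seen or recorded, the medical monitor must be called.

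**The sample.** The same schedule places haematology, chemistry and urinalysis at pre-dose of each injection. Footnote 3 allows an earlier draw: "Participants may have some assessments, such as HIV test, drug/alcohol screen, pregnancy test, haematology/chemistry/urinalysis and coagulation tests, done on the day before" each injection. This is an option, not a requirement.

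**The stop.** Section 7.1.1 states: "Discontinuation of study intervention for abnormal liver tests is required when" the liver algorithm is met. Appendix 6 sets the threshold at ALT ≥3×ULN, and its first action is "Immediately discontinue study intervention". Symptoms are not part of the criterion.

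**The stated protection.** For drug-induced liver injury, section 2.3.1 relies on this pairing: "Liver transaminases (ALT and AST) will be monitored throughout this study (refer to SoA) and the liver chemistry stopping criteria will be adopted".

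**The duty to read results.** Section 8.2.4: "The investigator must review the laboratory report, document this review, and record any clinically relevant changes". No time limit relative to the next dose is given.

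**The concern.** Cohort 4b has two CAB injections, so Injection 2 is the only long-acting dose left to withhold once Injection 1 has been given. A raised ALT without symptoms does not show on an ECG, a brief physical examination, vital signs or adverse-event questioning. A site could complete every item in footnote 2 and inject a participant whose sample, already drawn but not yet read, meets a mandatory stop.

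At stake is a further 300 mg depot dose that cannot be removed, in a healthy volunteer for whom section 2.3.2 expects no benefit from the drug. Injection 1 already commits that person to a depot and long follow-up, so the harm is added exposure. No endpoint, estimate or analysis is affected.

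**Working it through.** There is no figure in the plan to reproduce. The check sets the texts side by side, then sizes the gap.

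**1. Does any other text close the gap?**

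| Text | Why it does not require the result before Injection 2 |
|---|---|
| 1.3.3 footnote 2, call to the medical monitor | Applies to an abnormality already seen or recorded; an unread result is neither |
| 1.3.3 footnote 3, draw the day before | Optional, and sets no duty to read |
| 8.2.4, review of laboratory reports | No deadline relative to dosing |
| 7.1, Grade 3 laboratory rule | SAP Appendix 8 grades ALT 2.5 to <5×ULN as Grade 2, so ALT from 3 to <5×ULN is missed; the rule also needs investigator and sponsor agreement |
| 7.1, liver pausing rules | Cohorts 5 and 6 only |

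The oral lead-in offers a comparison. Footnote 3 of section 1.3.1 says outright that the Day 1 chemistry and haematology results are not needed before the first tablet. For the injection, 1.3.3 says nothing either way.

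**2. Which participants?** Cohort 4h has one injection. SAP section 2.3 records that Cohort 5 would receive no Injection 2 and that Cohort 6 was not needed. SAP section 3.2 describes an interim analysis timed before all of Cohort 4b finish the injection phase, by when the other cohorts will have completed their primary injection-phase assessments. That leaves Cohort 4b, planned at 24.

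**3. How long is the gap?** The last scheduled panel before the Injection 2 sample is Injection 1 Day 14 (SAP Appendix 3, Table 2). Injection 2 is due at Week 4 ± 3 days.

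- Nominal: 28 − 14 = 14 days
- Shortest: 25 − 14 = 11 days
- Longest: 31 − 14 = 17 days

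**4. What comes before the gap?** Six panels follow the first CAB dose: oral lead-in Days 2, 14 and 29, then Injection 1 pre-dose, Day 8 and Day 14. Only a rise that is new after the last of these is exposed.

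**5. Rough size.** The documents give no rate for ALT ≥3×ULN. The nearest figure is in section 2.3.1: six participants with suspected drug-induced liver injury, and programme exposure of "total exposure approximately 1909 people; 3640 person years to 31 December 2018". Assume a constant rate and that all 24 reach Injection 2.

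- Rate: 6 / 3640 = 0.00165 per person-year
- Time at risk, 14 days: 24 × 14 / 365.25 = 0.920 person-years
- Expected cases: 0.920 × 0.00165 = 0.0015
- At 11 days: 0.723 × 0.00165 = 0.0012
- At 17 days: 1.117 × 0.00165 = 0.0018

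The exact Poisson 95% limits for six events are 2.20 and 13.06.

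- Lowest: (2.20 / 3640) × 0.723 = 0.0004
- Highest: (13.06 / 3640) × 1.117 = 0.0040

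**The case against.** **The expected benefit is close to zero.** This stands. It caps the severity, and the case for acting rests on the low cost of the change.

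**The rate measures something else.** This also stands. The six cases were suspected drug-induced liver injury identified in HIV treatment and interaction studies, all in people who received oral CAB, while the 3640 person-years are given for the programme as a whole. The stop applies to ALT from any cause. The 0.0015 is an order of magnitude, not an estimate of the event.

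**More exposure may do little harm.** Section 2.2 reports no relationship between CAB concentrations and ALT or bilirubin changes in ATLAS and FLAIR. Section 4.2.4 finds no apparent link between adverse events and concentration in the 200 mg/mL programme. These reports soften the consequence. They do not remove the protocol's own instruction to stop.

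**Footnote 2 is a minimum, and 7.1.1 binds regardless.** True. A careful site would probably read the panel first, and the laboratory manual, which is not available here, may cover turnaround. But a stop can act only on a result that someone has read, and nothing visible makes that happen before the injection.

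**Stronger readings.** A reader might infer that footnote 2 permits laboratory results to be ignored. It does not; it is silent. A reader might also infer that hypersensitivity goes unchecked, since section 7.1 withdraws "Any participant developing a grade 2 or higher rash with concurrent fever, AST/ALT elevation or eosinophilia prior to the follow-up phase". The documents do not support that: the rash and fever are covered by the skin examination, temperature and adverse-event assessment already listed, and only the AST/ALT and eosinophil limbs depend on the laboratory. Nor is liver monitoring absent, given the six earlier panels.

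**Conclusion.** The point holds as a minor procedural gap. In Cohort 4b the pre-dose chemistry and haematology are scheduled at Injection 2, but no visible text requires the results to be seen before dosing. A new asymptomatic ALT ≥3×ULN arising after the Day 14 panel could therefore be read only after the last dose that 7.1.1 and Appendix 6 would have stopped.

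The ceiling is the planned 24 participants over a gap of about 11 to 17 days. The number still awaiting Injection 2 when the SAP was amended is not given. The number affected is very probably zero, but it cannot be calculated from the documents for ALT ≥3×ULN.

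The conclusion assumes that no unseen manual already imposes this check. The same list appears for the other cohorts, but it matters now only where a second injection can still be withheld.

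**What to change.** In section 1.3.3, draw the scheduled pre-dose chemistry and haematology sample on Injection 2 Day −1. Add to footnote 2, as a separate sentence so that its normal-limits standard does not extend to every analyte:

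*Before Injection 2, the ALT and bilirubin results from the pre-dose sample must be reviewed; do not inject if a participant-level liver stopping criterion in Section 7.1.1/Appendix 6 is met (ALT ≥3×ULN), and contact the medical monitor for any Grade 3 or higher laboratory abnormality.*

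The trigger should point to 7.1.1 and Appendix 6 and not to 7.1 as a whole, because 7.1 also holds cohort-level pausing rules and criteria that need investigator and sponsor agreement.

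The cost is one sentence, by amendment or clarification letter. There is no extra blood draw and no change to sample size or analysis. Footnote 3 already allows a day-before draw, Cohort 4b already has Day −1 procedures (section 8), and the tests are run locally (Appendix 2). The downside is that dosing may occasionally wait for laboratory turnaround, within the existing ±3-day window. If every Cohort 4b participant has already had Injection 2, the change can serve only later protocols that reuse this schedule.

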5. CCI [REDACTED]
[REDACTED]
[REDACTED]
6. AE assessment will include a brief, symptom-directed physical exam as needed.
7. A total of 38 PK samples will be collected through the injection phase and Follow-up.
8. Urine or plasma pregnancy testing to be performed pre-injection where relevant
9. HIV antibody test (either a laboratory or point of care test).
10. See Section 8.2.6.
11. See Section 6.1.2. CCI [REDACTED]
[REDACTED]
12. Participants will be asked to describe any preference for Injection 1 or 2 and provide reasons for their preference (if any). The CCI [REDACTED] will be completed 4 weeks after Injection 2.

1.3.4. CAB 400 mg/mL or CAB 200 mg/mL LA Injection Phase and Follow- up: Part 1 Cohort 4h (CAB 400 mg/mL or CAB 200 mg/mL with rHuPH20)

		Injection Phase																	Follow-up Phase										
Injection	Within 7 and/or 5 days of admission to the clinic ³	Inj Day 1							Inj Day 2	Inj Day 3	Inj Day 4	Inj Day 5	Inj Day 6	Inj Day 7	Inj Day 8	Inj Day 10	Inj Day 14	Inj Day 17	Inj Day 22	Inj Day 28 – proceed to follow-up	Week 4/ Day 28	Week 8	Week 12	Week 20	Week 28	Week 36	Week 44	Week 52 / EW ¹	
Procedures		Pre-dose ²	1 h	2 h	4 h	8 h	12 h	24 h																					
Permitted window for PK collection		Within 1 h prior to dosing	±15 min	±30 min	±1 h	±1 h	±2 h	±2 h	±2 h	±2 h	±2 h	±2 h	±2 h	±2 h	±2 h	±2 h	±1 day	±1 day	±1 day		±3 days	±3 days	±3 days	±3 days	±3 days	±3 days	±3 days	±3 days	
Interim Medical /Medication/ Drug / Alcohol History		X																											
Pregnancy Test ^{3,8}		X															X				X	X	X			X	X	X	
12-Lead ECG		X		X				X	X	X	X	X	X	X	X	X													
Testing for SARS-CoV-2	X ³														X ³														
HIV Test ^{3,9}		X																			X								X
Haematology; Clinical Chemistry; Urinalysis ³		X							X ¹³		X ¹³				X			X				X	X	X			X	X	X
Coagulation Tests ³		X																											X

		Injection Phase																Follow-up Phase									
Injection	Within 7 and/or 5 days of admission to the clinic ³	Inj Day 1						Inj Day 2	Inj Day 3	Inj Day 4	Inj Day 5	Inj Day 6	Inj Day 7	Inj Day 8	Inj Day 10	Inj Day 14	Inj Day 17	Inj Day 22	Inj Day 28 – proceed to follow-up	Week 4/ Day 28	Week 8	Week 12	Week 20	Week 28	Week 36	Week 44	Week 52 / EW ¹
Procedures		Pre-dose ²	1 h	2 h	4 h	8 h	12 h	24 h																			
Brief Physical Exam		X						X						X						X	X	X			X	X	X
Weight																				X				X			X
Vital Signs		X	X	X		X		X	X		X	X	X	X	X	X	X	X		X	X	X			X	X	X
Admit to clinic		X ³																									
Administer rHuPH20 followed by CAB 400 mg/mL or CAB 200 mg/mL ⁴		X																									
CCI																											
Provide diary card regarding injection site reactions		X																									
Discharge from the clinic														X ¹²													
Injection site reaction assessment ¹⁰			X	X	X	X	X	X	X	X	X	X	X	X	X	X	X	X		X	X	X	X	X	X	X	X
AE Assessment ⁶			X	X	X	X	X	X	X	X	X	X	X	X	X	X	X	X		X	X	X	X	X	X	X	X

		Injection Phase																	Follow-up Phase									
Injection	Within 7 and/or 5 days of admission to the clinic ³	Inj Day 1							Inj Day 2	Inj Day 3	Inj Day 4	Inj Day 5	Inj Day 6	Inj Day 7	Inj Day 8	Inj Day 10	Inj Day 14	Inj Day 17	Inj Day 22	Inj Day 28 – proceed to follow-up	Week 4/ Day 28	Week 8	Week 12	Week 20	Week 28	Week 36	Week 44	Week 52 / EW ¹
Procedures		Pre-dose ²	1 h	2 h	4 h	8 h	12 h	24 h																				
Concomitant Medication Review			X	X	X	X	X	X	X	X	X	X	X	X	X	X	X	X	X		X	X	X	X	X	X	X	X
Blood plasma PK Sampling ⁷		X	X	X	X	X	X	X	X	X	X	X	X	X	X	X	X	X	X		X	X	X	X	X	X	X	X
Blood plasma sampling (rHuPH20 immunogenicity) ¹¹		X															X				X							

- Participants will have PK monitoring up to and including Week 52 post last injection. Participants with undetectable CAB concentrations before this timepoint will be deemed to have completed follow up and return to the clinic for a last study visit at which activities specified for the Week 52/EW visit will be performed. Participants who withdraw from the study before week 52 post last injection will be asked to return to the site for a withdrawal visit.
- On Day 1, study personnel must verify the following pre-dose assessments to be within normal limits prior to injection: ECG, brief physical exam, vital signs, pregnancy test (negative; FRP only), AE assessment, and concomitant medication assessment. If a clinical abnormality, clinically significant AE, or prohibited medication that precludes injection is observed/recorded, the medical monitor must be contacted for further instruction.
- Participants may be admitted to the clinic before Injection Day 1. Any new Phase I unit participating in this study will adhere to the following SARS-CoV-2 testing procedures. **Where SARS-CoV-2 is circulating in the community**, participants should have one SARS-CoV-2 test approximately 1 week prior to admission to the clinic. A second test would be done upon admission; prior to the test result being known, participants should follow strict infection control procedures (PPE/social distancing) and should be isolated within an area of the unit to avoid exposure to COVID-19 negative participants until the test result is known. Once the test result is a confirmed negative, they can be released into the unit and follow infection control practices as per unit guidance. Any new Phase I unit participating in this study will adhere to the following SARS-CoV-2 testing procedures. A further test will be done upon discharge from the clinic (between Day 5 and Day 8 – see footnote 12). **Where SARS-CoV-2 is NOT circulating in the community**, SARS-CoV-2 testing prior to dosing may be performed within 5 days of admission to the clinic, and if participants are not admitted, they will be advised to avoid exposure to COVID-19 and self-quarantine until entrance to the unit while awaiting final testing clearance. Sponsor approval is required for site(s) to adopt SARS-CoV-2 testing within 5 days of admission to the clinic if study participants do not remain and isolate within the unit until test results are known. A further test is NOT required upon discharge from the clinic. Participants may have some assessments, such as HIV test, drug/alcohol screen, pregnancy test, haematology/chemistry/urinalysis and coagulation tests, done on the day before Injection Day 1.

4. Randomization to occur on Day 1 prior to the injection. CAB 400 mg/mL and CAB 200 mg/mL - injection dose of 400 mg SC. Participants receive 5000 U of rHuPH20 followed by CAB 200 mg/mL or 400 mg/mL formulation via a subcutaneous injection via a single butterfly needle. Due to a dead volume of 0.331 mL in the butterfly tube, a larger volume of CAB 200 mg/mL or 400 mg/mL formulation will be required. Therefore, 1.4 mL of CAB 400 mg/mL and 2.4 mL of CAB 200 mg/mL for injection will be used, and the exact doses of CAB 400 mg/mL and CAB 200 mg/mL administered will be 427.6 mg (1.069 mL) and 413.8 mg (2.069 mL), respectively.
5. **CCI** [REDACTED]
[REDACTED]
[REDACTED]
6. AE assessment will include a brief, symptom-directed physical exam as needed.
7. A total of 25 PK samples will be collected through the injection phase and Follow-up.
8. Urine or plasma pregnancy testing to be performed pre-injection where relevant
9. HIV antibody test (either a laboratory or point of care test).
10. See Section [8.2.6](#).
11. Plasma samples (K3-EDTA) for optional rHuPH20 immunogenicity analysis at pre-dose, Day 14 and Day 28. Analysis will be event-driven, (e.g. only if there are safety observations suggestive of an immune-mediated event).
12. Participants may be discharged from the clinic between Injection Day 5 and Injection Day 8. If participants are discharged prior to Injection Day 8, they would return to the clinic for assessments on the days specified in the SoA. **Where SARS-CoV-2 is circulating in the community**, participants should have a SARS-CoV-2 test on the day they are being discharged from the clinic.
13. No urinalysis needs to be performed on Days 3 and 5.

1.3.5. CAB 400 mg/mL or 200 mg/mL LA Injection Phase and Follow- up: Part 2 Cohorts 5 and 6

		Injection Phase																Follow-up Phase						
Injection 1 ¹⁰	Within 7 and/or 5 days of admission to the clinic ³	Inj 1 Day 1				Inj 1 Day 2	Inj 1 Day 3	Inj 1 Day 5	Inj 1 Day 6	Inj 1 Day 7	Inj 1 Day 8	Inj 1 Day 10	Inj 1 Day 14	Inj 1 Day 17	Inj 1 Day 22	Inj 1 Week 4	Inj 1 Week 6	Inj 1 Week 8	Inj 1 Week 10	Inj 1 Week 12 - proceed to Injection 2 Day 1	Follow-up post last injection			
Injection 2	Within 7 and/or 5 days of admission to the clinic ³	Inj 2 Day 1				Inj 2 Day 2	Inj 2 Day 3	Inj 2 Day 5	Inj 2 Day 6	Inj 2 Day 7	Inj 2 Day 8	Inj 2 Day 10	Inj 2 Day 14	Inj 2 Day 17	Inj 2 Day 22	Inj 2 Week 4	Inj 2 Week 6	Inj 2 Week 8	Inj 2 Week 10	Inj 2 Week 12 - proceed to follow-up	Week 12	Week 24	Week 40	Week 52/EW ¹
		Pre-dose ²	1 h	2 h	8 h	24 h																		
Permitted window for PK collection		Within 1 h prior to dosing	±15 min	±30 min	±1 h	±2 h	±2 h	±2 h	±2 h	±2 h	±2 h	±1 day	±1 day	±1 day	±1 day	±1 day	±1 day	±1 day	±1 day		±3 days	±3 days	±3 days	±3 days
Interim Medical / Medication/ Drug / Alcohol History		X																						
Pregnancy Test ^{3,8}		X										X					X				X	X	X	X
Triplicate 12-Lead ECG		X		X		X	X	X	X	X	X	X												

		Injection Phase																	Follow-up Phase			
Injection 1 ¹⁰	Within 7 and/or 5 days of admission to the clinic ³	Inj 1 Day 1 Inj 1 Day 2 Inj 1 Day 3 Inj 1 Day 5 Inj 1 Day 6 Inj 1 Day 7 Inj 1 Day 8 Inj 1 Day 10 Inj 1 Day 14 Inj 1 Day 17 Inj 1 Day 22 Inj 1 Week 4 Inj 1 Week 6 Inj 1 Week 8 Inj 1 Week 10 Inj 1 Week 12 - proceed to Injection 2 Day 1																	Follow-up post last injection			
Injection 2	Within 7 and/or 5 days of admission to the clinic ³	Inj 2 Day 1 Inj 2 Day 2 Inj 2 Day 3 Inj 2 Day 5 Inj 2 Day 6 Inj 2 Day 7 Inj 2 Day 8 Inj 2 Day 10 Inj 2 Day 14 Inj 2 Day 17 Inj 2 Day 22 Inj 2 Week 4 Inj 2 Week 6 Inj 2 Week 8 Inj 2 Week 10 Inj 2 Week 12 - proceed to follow-up																	Week 12	Week 24	Week 40	Week 52/EW ¹
		Pre-dose ²	1 h	2 h	8 h	24 h																
Testing for SARS-CoV-2	X ³								X ³													
HIV Test ^{3,9}		X																X			X	
Haematology; Clinical Chemistry; Urinalysis ³		X				X ¹¹	X ¹¹	X ¹¹		X		X	X		X		X	X	X	X	X	
Coagulation Tests ³		X											X								X	
Brief Physical Exam		X				X		X		X			X		X		X	X		X	X	
Weight		X																X	X		X	
Vital Signs		X	X	X	X	X	X	X	X	X	X	X	X	X	X	X	X	X	X	X	X	
Admit to clinic		X ³																				

		Injection Phase																	Follow-up Phase							
Injection 1 ¹⁰	Within 7 and/or 5 days of admission to the clinic ³	Inj 1 Day 1					Inj 1 Day 2	Inj 1 Day 3	Inj 1 Day 5	Inj 1 Day 6	Inj 1 Day 7	Inj 1 Day 8	Inj 1 Day 10	Inj 1 Day 14	Inj 1 Day 17	Inj 1 Day 22	Inj 1 Week 4	Inj 1 Week 6	Inj 1 Week 8	Inj 1 Week 10	Inj 1 Week 12 - proceed to Injection 2 Day 1	Follow-up post last injection				
Injection 2	Within 7 and/or 5 days of admission to the clinic ³	Inj 2 Day 1					Inj 2 Day 2	Inj 2 Day 3	Inj 2 Day 5	Inj 2 Day 6	Inj 2 Day 7	Inj 2 Day 8	Inj 2 Day 10	Inj 2 Day 14	Inj 2 Day 17	Inj 2 Day 22	Inj 2 Week 4	Inj 2 Week 6	Inj 2 Week 8	Inj 2 Week 10	Inj 2 Week 12 - proceed to follow-up	Week 12	Week 24	Week 40	Week 52/EW ¹	
		Pre-dose ²	1 h	2 h	8 h	24 h																				
Administer CAB 400 mg/mL or CAB 200 mg/mL LA ⁴		X																								
CCI																										
Provide diary card regarding injection site reactions		X																								
Discharge from the clinic											X ¹⁰															
Injection site reaction assessment ¹²			X	X	X	X	X	X	X	X	X	X	X	X	X	X	X	X	X	X		X	X	X	X	

		Injection Phase																			Follow-up Phase			
Injection 1 ¹⁰	Within 7 and/or 5 days of admission to the clinic ³	Inj 1 Day 1				Inj 1 Day 2	Inj 1 Day 3	Inj 1 Day 5	Inj 1 Day 6	Inj 1 Day 7	Inj 1 Day 8	Inj 1 Day 10	Inj 1 Day 14	Inj 1 Day 17	Inj 1 Day 22	Inj 1 Week 4	Inj 1 Week 6	Inj 1 Week 8	Inj 1 Week 10	Inj 1 Week 12 - proceed to Injection 2 Day 1	Follow-up post last injection			
Injection 2	Within 7 and/or 5 days of admission to the clinic ³	Inj 2 Day 1				Inj 2 Day 2	Inj 2 Day 3	Inj 2 Day 5	Inj 2 Day 6	Inj 2 Day 7	Inj 2 Day 8	Inj 2 Day 10	Inj 2 Day 14	Inj 2 Day 17	Inj 2 Day 22	Inj 2 Week 4	Inj 2 Week 6	Inj 2 Week 8	Inj 2 Week 10	Inj 2 Week 12 - proceed to follow-up	Week 12	Week 24	Week 40	Week 52/EW ¹
		Pre-dose ²	1 h	2 h	8 h	24 h																		
AE Assessment ⁶			X	X	X	X	X	X	X	X	X	X	X	X	X	X	X	X	X		X	X	X	X
Concomitant Medication Review		X	X	X	X	X	X	X	X	X	X	X	X	X	X	X	X	X	X		X	X	X	X
Blood plasma PK Sampling ⁷		X	X	X	X	X	X	X	X	X	X	X	X	X	X	X	X	X	X		X	X	X	X

- Participants will have PK monitoring up to and including Week 52 post last injection. Participants with undetectable CAB concentrations before this timepoint will be deemed to have completed follow up and return to the clinic for a last study visit at which activities specified for the Week 52/EW visit will be performed. Participants who withdraw from the study before Week 52 post last injection will be asked to return to the site for a withdrawal visit.
- On Day 1, study personnel must verify the following pre-dose assessments to be within normal limits prior to injection: triplicate 12-lead ECG, brief physical exam, vital signs, pregnancy test (negative; FRP only), AE assessment, and concomitant medication assessment. If a clinical abnormality, clinically significant AE, or prohibited medication that precludes injection is observed/recorded, the medical monitor must be contacted for further instruction.
- Participants may be admitted to the clinic before Injection 1 Day 1 and Injection 2 Day 1. Any new Phase I unit participating in this study will adhere to the following SARS-CoV-2 testing procedures. **Where SARS-CoV-2 is circulating in the community**, participants should have one SARS-CoV-2 test approximately 1 week prior to admission to the clinic. A second test would be done upon admission; prior to the test result being known, participants should follow strict infection control procedures (PPE/social distancing) and should be isolated within an area of the unit to avoid exposure to COVID-19 negative participants until the test result is known. Once the test result is a confirmed negative, they can be

released into the unit and follow infection control practices as per unit guidance. A further test will be done on Day 8 upon discharge from the clinic. **Where SARS-CoV-2 is NOT circulating in the community**, SARS-CoV-2 testing prior to dosing may be performed within 5 days of admission to the clinic, and if participants are not admitted, they will be advised to avoid exposure to COVID-19 and self-quarantine until entrance to the unit while awaiting final testing clearance. Sponsor approval is required for site(s) to adopt SARS-CoV-2 testing within 5 days of admission to the clinic if study participants do not remain and isolate within the unit until test results are known. A further test is NOT required on Day 8 upon discharge from the clinic. Participants may have some assessments, such as HIV test, drug/alcohol screen, pregnancy test, haematology/chemistry/urinalysis and coagulation tests, done on the day before Injection 1 Day 1 and Injection 2 Day 1.

4. Randomization in Part 2 to occur on Day 1 prior to the first injection. CAB 400 mg/mL – (dose determination by SRT following cohort 1) injection via *gluteus medius* on Day 1 and Week 12 (\pm 3 days for second injection). Active control participants will receive CAB 200 mg/mL matched on volume to CAB 400 mg/mL participants.
